## **16.5. Adherence Assessment and Intervention**

At each study visit, adherence will be assessed by self-report metrics via CASI. DBS specimens will be performed for real-time intraerythrocytic TFV-DP drug level assays.

### **16.5.1. Real-time intraerythrocytic drug levels**

Blood will be collected for intraerythrocytic TFV-DP drug level assays at each follow-up visit. Prior pharmacokinetic/pharmacodynamics studies have established levels for categorization of dosing for interpretation of DBS levels. Given the high adherence requirement for women to achieve protective levels, a threshold of 1050 fmol/punch corresponding to 6 or more doses per week will be used as the threshold for optimal adherence (28, 60). Levels below this threshold will be considered to represent suboptimal adherence and will trigger intensification of adherence support as outlined below.

### **16.5.2. iTAB System**

iTAB is a personalized, two-way, text-messaging intervention developed to improve medication adherence in diverse difficult-to-treat cohorts such as HIV-infected with comorbid psychiatric (i.e. bipolar disorder) and substance use disorders (i.e. methamphetamine dependence) and more recently for PrEP adherence (61-63). The system has several components identified in the broader literature as integral to long-term engagement and effectiveness of text messaging interventions in supporting medication adherence, including: 1) interactive, two-way, communication; 2) individually tailored message content; and 3) delivery of messages to match dosage timing (64, 65). To personalize our text-messaging interactions, we will use a combination of focus-group derived content in certain thematic areas (61), as well as allow participants to create their own messages. Patients develop brief statements called “implementation intentions” integrated into text messages, which ensures personalization capitalizing on the persuasiveness of their own language and phrasing, “When I brush my teeth, I will take my PrEP.”

The iTAB system builds from a variety of behavioral theories used in HIV prevention studies, including the Health Belief Model, Social Cognitive Theory, and the Theory of Planned Behavior (TPB) (66, 67). While these theories differ in some aspects, they also contain a number of shared underlying constructs (68). For example, interventions that focus on the intention to change risk behaviors via changes in self-efficacy and perceived behavioral control (aspects of TPB) are associated with greater condom use (69, 70). Our iTAB intervention primarily targets individual or intra-personal aspects of behavior and is directed primarily by the TPB, which suggests that behavior is driven by: i) attitudes toward the proposed behavior, ii) social norms/perceptions of others, and iii) beliefs that they can control the behavior, which feed into behavioral / implementation intentions (e.g., “I plan to take my PrEP”).

iTAB has found to be associated with high adherence and valid as a measure of self-reported adherence in CCTG 595, an open-label, two-arm, controlled, randomized 1:1 clinical trial of iTAB versus standard of care (no iTAB) as a demonstration project evaluating retention and adherence to PrEP in 400 MSM and transgender women over 48 weeks. In a preliminary analysis of intracellular TFV-DP levels in Week 12 DBS among the first 152 participants in the iTAB arm (71), we found that adherence in the iTAB arm was high with a

mean TFV-DP of 1352 fmol/punch, which equates to taking 6 of 7 doses of PrEP a week. Since CCTG 595 is an ongoing study, the comparison of iTAB to a control arm that did not receive iTAB text has not been performed yet. The preliminary data also show a significant correlation between TFV-DP concentrations and proportion of positive (“Yes, I took my meds.”) iTAB responses ( $r=0.26$ ,  $p=0.01$ ) supporting iTAB as a valid measure of adherence. These findings support the use of iTAB as a valid self-reported measure for adherence that can discriminate between adequate and inadequate PrEP adherence.

In this study, all participants will receive text messaging through the iTAB system. At the baseline visit, the study coordinator will introduce the participant to the iTAB texting system and provide training on iTAB framework for texting supportive reminder messages and tracking adherence. If a participant does not have unlimited text messaging, the study will provide participant reimbursement to pay for unlimited text messages. In cases where a participant does not have a phone, an appropriate cell phone with an unlimited texting plan will be provided.

Daily dosing reminders will be sent for the duration of the study. Both reminder timing and message content can be individualized and will be arranged at the baseline visit. The study coordinator will work with the participant to select and refine 10 personal reminders from a list of pre-determined reminders that cover various themes shown to be effective in improving adherence (i.e., social support, loss frame, health gain) as well as 5 categories of factoids (i.e., food, history, science). Participants will receive 2 personal reminders and 5 factoids each week for the duration of the study. These themes will be developed through focus groups and targeted group feedback. Participants can choose to create their own reminders if they prefer, and messages can be modified throughout the course of the study. The coordinator will work with each participant individually to ensure that adherence reminders are programmed to be sent at times consistent with when the patient typically takes her medication. Reminder times can vary for different days of the week to accommodate for changes in schedule (e.g., 8 M-F, and 10 AM on Sat/Sun). Once the preferred dosing time is identified, the text reminder system is automated. Patients will confirm medication taking via text responses to the personalized reminders. If a participant does not respond on three consecutive occasions, a high alert message (chosen by the participant) will be sent. If the participant does not respond to this message, the study coordinator will initiate phone calls to contact the participant to determine reason for no-reply. At any point, if a participant initiates a text that is not one of the expected responses, the study team will review that text and contact the subject if there is a concern. Participants will be informed not to use texting for emergencies. The content/reasons for iTAB requests for assistance will be documented and summarized post study,

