### **27.3. Management of Suspected Acute Seroconversion (Primary HIV Infection - PHI)**

Should an enrolled participant present with signs and symptoms consistent with PHI, this should trigger immediate HIV EIA and Viral Load (VL) or NAT testing; any positive result should prompt immediate resistance testing and referral to HIV specialty care. Participants who seroconvert within the protocol will undergo evaluation as in the schedule of events (see Section 19) and be provided assistance as needed to establish care. If the subject is currently taking TDF/FTC a third antiretroviral would be recommended as soon as possible. If there is a delay in obtaining care then TDF/FTC should be discontinued until an adequate antiretroviral regimen can be started. If the seroconverting individual is not taking TDF/FTC they will be advised not to take TDF/FTC until a complete regimen can be acquired.

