**28. CRITERIA FOR DISCONTINUATION**

**28.1. Temporary Medication Interruption**

Attempts should be made to avoid temporary interruption.

Symptoms should be managed aggressively and proactively in an attempt to avoid discontinuation, provided there is no laboratory evidence of toxicity and any symptoms are Grade 1 or 2. In the event of symptomatic Grade 3 or any Grade 4 toxicity, TDF/FTC should be discontinued immediately, the only exception being a toxicity indisputably not attributable to TDF/FTC administration, with the permission of the protocol PI.

In the event of inadvertent discontinuation due to missed appointments, loss of medication, or other unforeseen circumstances, treatment should be resumed as rapidly as possible. Treatment should ONLY be reinstated in the absence of signs/symptoms of PHI (Table 1 above).

If the amount of time since last dosing of TDF/FTC exceeds 14 days when the participant wishes to reinitiate PrEP, a negative rapid HIV EIA and HIV VL should be documented PRIOR to PrEP reinitiation. If a serum creatinine has not been performed for study purposes within the past 30 days, serum creatinine too should be repeated (and Creatinine Clearance calculated and documented) prior to medication re-initiation.

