**28.2. Permanent Medication Discontinuation**

Permanent medication discontinuation prior to 48 weeks of treatment should be limited to participants who withdraw consent, have laboratory evidence of acute or chronic HIV infection, are so advised by HIV-treatment experts, or have severe toxicity as noted above.

Such participants should continue to be followed per the protocol SOE (Cohort or seroconversion, as appropriate), even though they are no longer taking study medication.

Additionally, participants who have persistently low TFV-DP levels (<1050 fmol/punch), are referred for targeted iNSC (first instance) and PrEP-STEPS (if followed by a suboptimal (<1050 fmol/punch) TFV-DP level at subsequent visit(s)). Refusal/failure to participate in PrEP-STEP programming by attending  $\geq 1$  visit within 30 days of request by study staff may be considered for medication discontinuation in discussion with the Protocol Chairs.

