#### Hypothesis II

Intracellular TFV-DP concentrations levels will correlate with self-reported adherence by daily texting through iTAB,

For the primary analysis, we will measure adherence using a drug level cutoff consistent with 6 or more doses per week, as measured by TFV-DP level > 1050 fmol/punch at weeks 4, 12, 24, 36 and 48. This will be in the as-treated group who are on-PrEP (censoring those on permanent or temporary discontinuation). A descriptive analysis of the proportion of women achieving adequate adherence by week of study will be conducted. Baseline versus 48 weeks proportion of adherence will be compared via Fisher's exact test.

**In order to examine drug adherence surrounding the implementation of intensified interventions specific to women receiving targeted iNSC and those receiving PrEP-STEPS we will compare the change in levels pre- and post-intervention.**

Additional sensitivity analyses will be performed using alternative cutoffs of adherence. Intracellular FTC-TP levels will be compared to TFV-DP for discrepancy of recent dosing that would be reflective of the short half-life of FTC (past day) versus the past week of dosing that is informed by the long half-life of TDF.

Subgroup analysis will compare adherence and other outcomes between risk categories of women (e.g. serodiscordant partnerships with and without conception intentions, partner of elevated HIV risk, sex worker, recent STI, injection drug use, PEP users).

Adherence will be measured by self-report using daily text messaging through iTAB. We will validate iTAB reported adherence in women using the TFV-DP levels for correlation with the proportion of positive responses in the 34 days prior to the drug level (i.e. two half lives of TDF) in week 12, 24, 36 or 48 using the Spearman correlation coefficient.

The average days of adherence per week during this time will be calculated as number of days reporting doses taken in past 35 days divided by 35 multiplied by 7 and rounded to the nearest whole number. For each number of days per week of adherence (i.e. 0, 1, 2,3, 4,

5,6 and 7) the TFV-DP will be reported from mean (95% confidence interval) and median (IQR).

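### Automated daily dosing reminders have no exception for women whose TDF/FTC has been held or stopped but who stay in follow-up

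*Combined protocol and SAP*

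**What the plan says.** On texting, section 16.5.2 (iTAB System) is unconditional: "Daily dosing reminders will be sent for the duration of the study". It adds: "Once the preferred dosing time is identified, the text reminder system is automated". After three consecutive non-responses a high-alert message goes out. If that is also unanswered, "the study coordinator will initiate phone calls to contact the participant to determine reason for no-reply".

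On stopping drug while on study:

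- Section 28.1: "In the event of symptomatic Grade 3 or any Grade 4 toxicity, TDF/FTC should be discontinued immediately", with one exception that needs the protocol PI's permission. Section 27.1.1 is to similar effect.
- Section 27.1.2 stops drug for a confirmed fall in creatinine clearance, and section 27.1.3 interrupts it for certain severe diarrhea.
- Section 27.3, for a seroconverter taking TDF/FTC whose access to care is delayed: "TDF/FTC should be discontinued until an adequate antiretroviral regimen can be started". A seroconverter not taking it is advised against taking it until a complete regimen is available.
- Section 28.2, for permanent discontinuation: "Such participants should continue to be followed per the protocol SOE".

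On counseling, section 16.5.3 does provide for women off drug: only the non-PrEP part of iNSC is delivered to them.

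**The concern.** These instructions meet in the same woman. She has been told to stop, she is still on study, and an automated system is set to prompt her each day and to chase her if she falls silent. The plan does not say which instruction governs the texts.

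What is at stake is mainly safety and clarity of conduct. Section 16.4 dispenses 8- or 12-week supplies after the first month, so a woman told to stop may still have tablets. Section 28.3 mentions return of unused drug only under program discontinuation. Section 28.1 requires a negative HIV antibody test and viral load before restarting after more than 14 days off drug. A dosing prompt during that time works against a check the protocol itself imposes.

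There is a smaller data issue. Without recorded off-drug dates, a reply that no dose was taken during a directed hold looks the same as a missed dose.

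**Working it through.** **1. The sections side by side.**

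| Situation | Drug | Still followed? | Counseling | Texts |
|---|---|---|---|---|
| Toxicity, renal or diarrhea hold (27.1.1–27.1.3, 28.1) | Held or stopped | Yes, monitored until resolution | Non-PrEP part of iNSC (16.5.3) | No rule |
| Seroconversion with delayed care (27.3) | Stopped | Yes, seroconversion schedule (27.4) | Linkage services (27.4) | No rule |
| Permanent discontinuation (28.2) | Stopped | Yes, schedule of events | Non-PrEP part of iNSC (16.5.3) | No rule |

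The last column is empty throughout, so the general sentence in 16.5.2 is the only one that applies.

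**2. How many texts this could mean.** The plan gives no figure. Section 4 sets adherence support at 48 weeks, and section 16.5.2 sets the weekly content at 2 personal reminders and 5 factoids. For a woman who stops at week 12 and is followed to week 48:

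- weeks exposed: 48 − 12 = 36
- daily texts: 36 × 7 = 252
- personal reminders: 36 × 2 = 72
- factoids: 36 × 5 = 180 (check: 72 + 180 = 252)

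This is a ceiling for one hypothetical woman. The text does not say how far a factoid message urges dosing.

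**3. Does the gap also spoil the iTAB score?** Section 30.2 defines average days per week as "number of days reporting doses taken in past 35 days divided by 35 multiplied by 7", rounded, and reports TFV-DP for each value from 0 to 7. Take a 14-day hold inside the window, with every other dose taken and reported:

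- score as written: (35 − 14)/35 × 7 = 4.2, which rounds to 4
- score if divided by days on prescribed drug: 21/21 × 7 = 7
- TFV-DP if the hold ends at sampling, using the 17-day half-life in section 10: 2^(−14/17) = 0.565 of its starting level

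The table relates drug level to doses actually reported. A hold day is a true no-dose day, and the drug level falls with it. The fixed divisor puts her in row 4. Dividing by prescribed days would put a woman at a little over half her usual level into row 7 and blur the table. For the same reason, hold days do not by themselves bias the Spearman correlation.

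**4. Does it reach the drug-level primary analysis?** No. The analysis of TFV-DP above 1050 fmol/punch does not use iTAB, and section 30.2 censors women on temporary or permanent discontinuation from it. Whether that censoring extends to the iTAB analyses is not stated.

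**The case against.** The strongest reply is that the contradiction is inferred from silence. Section 16.5.2 says "messages can be modified throughout the course of the study". Non-reply leads to a call whose purpose is to find out why, and staff review unexpected texts. A coordinator could therefore learn of the stop and act. The MOPS, which is not available here, holds operational detail for related components and might cover this.

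Part of that stands. The documents do not show that any woman will in fact be prompted against advice; they show only that no rule prevents it. The rest is weaker. The sentence about modifying messages concerns the reminders a woman chooses or writes, and describes no pause. The call comes only after repeated silence, so a woman who keeps replying that she took no dose never triggers it. Section 16.5.2 does not refer to the MOPS, whereas section 16.5.3 does.

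It is also fair that interruptions may be few: section 28.1 asks sites to avoid them, and the stop under 27.3 depends on delayed care.

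A reader might infer more than the documents support:

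- *That a PEP course is a further example.* Section 16.1 speaks of resuming protocol participation afterwards, which suggests that participation is suspended.
- *That iTAB is a co-primary endpoint.* It is part of the primary objective (section 5.1), but section 4 defines the primary outcome by TFV-DP.
- *That hold days corrupt the adherence score.* Step 3 of the working shows why not. Section 30.2 sets out no analysis linking that score to objective 5.3.2.

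**Conclusion.** The point holds as an unreconciled contradiction in study conduct. Section 16.5.2, read literally, keeps dosing reminders and the no-reply cascade running for women whose drug has been held or stopped under sections 27.1.1 to 27.1.3, 27.3 or 28.1 and who remain in follow-up, permanently stopped women expressly so under 28.2. Section 16.5.3 shows that the authors allowed for women off drug in counseling, which makes the omission for texting look like an oversight.

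The size is bounded rather than estimated: no hold frequency is given, and 252 texts, mostly factoids, is the ceiling in the week-12 example. That figure assumes the stated weekly mix is kept and nobody intervenes. The drug-level primary analysis and the 35-day score are not undermined. It is worth correcting because it bears on safety and costs little. A later SAP, which section 30 says takes precedence on analysis, could settle how iTAB data are handled but cannot govern live messages.

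**What to change.** Reconcile section 16.5.2 with sections 27.1.1 to 27.1.3, 27.3, 28.1 and 28.2, so that dosing reminders and the no-reply cascade follow the participant's current on-drug or off-drug status as determined under those sections. This takes no position on when drug should be held, stopped or restarted. Record the off-drug dates in iTAB.

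In the analysis, keep the fixed 35-day divisor for the table of TFV-DP by reported days. Use the logged dates only to identify provider-directed hold days if iTAB responses are separately summarised over time as adherence to prescribed dosing (objective 5.3.2). The SAP should also state whether the censoring in section 30.2 applies to the iTAB analyses.

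The cost is a sentence in the protocol, a status setting in the texting system and a pair of dates per interruption. The one downside is that text contact may lapse during a hold unless non-dosing messages continue.

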### 16.5.3. **Integrated Next Step Counseling, Targeted Integrated Next Step Counseling and PrEP-STEPS**

iNSC has two yoked components- a focused discussion of all things the person is doing or thinking of doing to protect their sexual health besides PrEP which then turns to discussing continued desire for PrEP as part of one’s protection plan, and, if so, current approaches to ensuring dosing in the present context/demands of participant’s life. Thus, regardless of whether or not the participant is receiving PrEP at any clinical visit, one (just the non-PrEP portion) or both parts of iNSC are implemented. During the first PrEP dispensation visit, the focus of the discussion is on preparing participants for adherence through enhancing literacy around PrEP and adherence, formulating a concrete plan for daily dosing and brainstorming potential barriers and discussing what to do if side-effects are experienced. The groundwork for discussing sexual health protection and approach that the study will adopt with an invitation for participants to fully engage in discussions and

openly share PrEP experiences and desires. Subsequent visits follow basic process where experiences are discussed, participants are asked about their sense of what, if anything, would make sexual health protection (non-PrEP strategies) easier or more manageable, ways to meet those needs explored, strategies discussed and a plan identified by the participant, which then transition to checking in with whether or not PrEP is still something they want as part of their plan (or if they want to add it if eligible and not on PrEP), and if so, PrEP dosing experiences are explored, needs identified, strategies discussed and a plan developed. Discourse is documented and will be summarized at the end of the study,

The main difference between iNSC and targeted iNSC focused on exploring whether or not PrEP is something the participant wants to continue with (given low drug level and relatedly low afforded PrEP benefit), and if so a strengths-based exploration (when dosing did occur, what facilitated it) precedes exploration of specific barriers to dosing (what specifically prevented consistent dosing), needs are identified, strategies discussed and an adherence plan created. Because participants all engage in iTAB, plans will also emphasize use of iTAB to ask for help. Participants no longer interested in PrEP will be engaged in discussion around that decision and their plan for how to stay HIV negative using other strategies discussed.

PrEP-STEPS is a four-session weekly intervention with two subsequent monthly booster sessions modeled after an evidence-based ART adherence intervention (LifeSteps) which is a Cognitive Behavioral Therapy (CBT)-based counseling approach to facilitate PrEP adherence. This program will be deployed at in-person sessions and is the highest intensity level intervention.

The 3 interventions will be used as three “stages” or levels of intensity of adherence support. One intervention is deployed for a given participant, titrated based on the history and chronology of real-time measured DBS TFV-DP levels.

All participants will receive iNSC at the baseline/entry visit and at all subsequent visits [see the MOPS for structure of the standard iNSC intervention]. Suboptimal adherence (TFV-DP levels of <1050 fmol/punch (representing fewer than mean 6-7 daily doses per week)) will trigger “targeted iNSC” which will be implemented when drug levels are obtained by the site- typically about 10 days after the clinic visit (72). Participants in this sub-optimal range are contact by the counselor, informed of their results and asked to come in for a specific conversation (targeted iNSC). This first level of more intensive support may be deployed by telephone or in person. There will not be additional compensation for participating in these sessions. Details of the targeted iNSC intervention are provided in the MOPS. If this is a repeat sub-optimal level the counselor schedules the participant for the first of 4 (+2 booster) PrEP-Steps sessions.

Details of the PrEP-STEPS Program with Content Optimized for Women program are provided in the MOPS.

All sites will be trained in the standard iNSC, targeted iNSC, and PrEP-STEPS interventions prior to initiation of participant enrollment. A booster-training will be scheduled once sites are operational. Regular conference calls will be arranged between the protocol adherence teams and site staff, and the protocol adherence consultant will be available for questions and/or troubleshooting as needed during study conduct. Participants will be asked for additional consent to have their adherence support sessions audio-recorded, and a subset of these audio recordings will be reviewed by the adherence consulting team for fidelity to the intervention; such audio recordings will be destroyed after review.

Refusal to participate in adherence interventions may be sufficient reason for participant to be considered for PrEP medication discontinuation, at the discretion of the Protocol Chairs.

